22.7 Reporting of Serious Adverse Events

All investigators must report both expected (protocol-defined) and unexpected serious adverse events. All serious protocol defined adverse events must be reported directly to the clinical center's IRB and the sponsor within 10 working days of knowledge of the event, or as dictated by the specific IRB policy, whichever is sooner. All unexpected serious adverse events must be reported to the sponsor within 24 hours of knowledge of the event and the clinical center's IRB as dictated by the specific IRB policy.

22.8 Eliciting adverse effect information

Investigators are responsible for preparing and submitting all reports as summarized on Table 1.0.

Case Report Forms should be entered within 10 days after the corresponding visit. Investigators are responsible for notifying the Sponsor of any changes to previously reported data. Upon request of the reviewing IRB, FDA, the Investigator must provide accurate, complete, and current information about any aspect of the study.

22.9 Table 1.0: Investigator Report Requirements

Report title/description	Requirement(s)	Submit to:
Adverse events (AE)	Immediately but no later than 10 days of becoming aware	Sponsor
Serious Adverse Event (SAE)	Report should be submitted immediately after the Investigator first learns of the event but no longer than 10 days hours	Sponsor If applicable, IRB
Unanticipated Adverse Device Effect (UADE)	Report should be submitted immediately after the Investigator first learns of the event but no longer than 10 working days	Sponsor IRB
Withdrawal of IRB approval	Report must be submitted immediately after the Investigator learns of the withdrawal but no longer than 5 working days.	Sponsor
Progress Report	Report must be submitted annually, or as required by the IRB, for the duration of the clinical study. The Sponsor may also prepare this report.	If applicable, IRB
CIP Deviations	Deviations from the investigational plan must be approved by the Sponsor prior to implementation NOTE: If the deviation affects the scientific soundness of the CIP or the rights, safety or welfare of the Subjects, the deviation must be approved by the Sponsor and IRB, if applicable.	Sponsor If Applicable IRB
	In the event that a CIP deviation occurs and the sponsor cannot be notified ahead of time (e.g., if the notification was to protect the life or physical well-being of the Subject),	Sponsor IRB

22.9 Anticipated or Potential Adverse Events

The list below provides anticipated or potential adverse events that may occur during the study. The potential adverse events are those that are expected to occur during the study because they are associated with the surgical procedure, stress-induced tests (e.g. TEE/TOE, TTE, MSCT scan, exercise tolerance, etc.), or the heart failure population over time. It is anticipated that subjects may require temporary medical and/or mechanical hemodynamic support in the peri and/or early post-op period. These events are not considered adverse events.

- Abnormal Lab values
- Allergic Reaction to Anesthetic, Anticoagulant Therapy, Contrast or Cobalt Chromium
- Anaphylactic Shock or Toxic Reaction
- Anemia
- Angina
- Annulus Rupture/ A-V Groove Disruption
- Aortic Valve Impairment/Damage
- Arrhythmias
- Atrial Fibrillation
- Atrio-ventricular Node Block
- A-V fistula or pseudo-aneurysm
- Bleeding diathesis
- Cardiac Arrest
- Cardiac Failure or Decompensation
- Cardiac Perforation
- Cardiac Tamponade/ Pericardial Effusion
- Cardiogenic Shock
- Chordal Rupture

- Conduction System Injury (defect) which may require pacemaker
- Conversion to Open Sternotomy
- Coronary Artery Obstruction
- Death
- Dissection, Any Vessel
- Dyspnea
- Edema
- Electrolyte Imbalance
- Electro-mechanical Dissociation
- Embolization including air, particulate, calcific material, or thrombus
- Emergent PCI
- Emergent Cardiac Surgery
- Endocarditis
- Esophagus Irritation/Perforation (TEE related)
- Fever
- Frame Strut Fracture
- GI Bleeding
- Heart Failure

SITRAL

Baylor Scott & White Research Institute

- Hematoma
- Hemolysis / Hemolytic Anemia
- Hemorrhage require transfusion/surgery
- Infection at the access site
- Inflammation
- Leaflet tearing
- Left Ventricle Failure
- Local and Systemic Infection
- LVOT Obstruction
- Mal-positioning of Prosthesis
- Multi-system Failure
- Myocardial Infarction
- Myocardial Ischemia
- Pacemaker Implantation
- Pannus Formation
- Papillary Muscle Damage
- Peripheral Ischemia
- Pleural effusion
- Pneumonia
- Prosthesis Dislodgement/Embolization
- Prosthesis Leaflet Entrapment

- Prosthesis Migration
- Prosthesis Paravalvular Leak
- Prosthesis Regurgitation
- Prosthetic Valvular Endocarditis
- Prosthetic Valvular Thrombosis
- Pulmonary Edema
- Pulmonary Vein Obstruction
- Reintervention or reoperation
- Renal Failure or Insufficiency
- Respiratory Failure
- Retroperitoneal Bleed
- Septicemia
- Stroke, TIA, or other Neurological Event
- Structural Deterioration
- Systolic Anterior Motion
- Thromboembolism
- Valve Stenosis
- Vascular trauma, dissection, or occlusion
- Ventricular Perforation by Frame
- Vessel Spasm
- Wound Dehiscence

22.10 Risk Minimization

Efforts to minimize risks associated with performing the procedure include the following:

- A. Selection of qualified Investigators
- B. Comprehensive Investigator training to insure that Investigators have a thorough knowledge of the CIP and the proper technique for implantation of the study device, including the following elements of instruction:

- Providing CIP training to all Investigators and study staff noted on the Delegation of Authority log (DOA)
- 2. Clearly defining the subject inclusion and exclusion criteria
- 3. Monitoring echocardiographic and hemodynamic parameters during placement of the implant
- 4. Ensuring data collection is consistent with the CIP
- 5. Ensuring treatment and follow-up of subjects is consistent with the CIP and standard and current medical practice

22.11 Potential Benefits

The clinical benefits of using the SAPIEN 3 valve in subjects with mitral annular calcification (MAC) associated with mitral stenosis and/or regurgitation are not known at the present time. There are no guaranteed benefits from participation in this clinical study and being treated with the study device.

Mitral valve replacement with the SAPIEN 3 valve may result in one or more of the following benefits for subjects typically considered high risk or inoperable for surgical MVR: decrease in mitral stenosis, decrease in mitral regurgitation, acute alleviation of symptoms related to mitral insufficiency and/or stenosis, and/or improved morbidity and mortality. Information gained from the conduct of this study may be of benefit to other people with the same medical condition in the future as the indication for the system is expanded.

23.0 STATISTICAL ANALYSIS & DATA MANAGEMENT

To describe procedural success and device success at 30 days, and subject success at 12 Months descriptive statistics (e.g. percentage) and plots will be estimated.

All tasks will be performed in compliance with HIPAA regulations. Patients' identifiers will be encrypted for study data shared with other study personnel. All data for the proposed study will be stored in the

February 26, 2016 Protocol Version 1.1

Confidential

secure database we will develop and periodic back-up will protect against catastrophic loss. All hard copy materials (summary printouts) will be stored by the principal investigator in locked file cabinets; disks and other removable storage media files will be stored as per HIPAA regulations. The Principal Investigator will be responsible for the data management operations.

24.1 ROLE OF BAYLOR RESEARCH INSTITUTE AS CLINICAL AND DATA COORDINATING CENTER

Baylor Research Institute is the sponsor of this study. The Sponsor is responsible for ensuring that this study will be conducted in compliance with all applicable U.S. Federal regulations pertaining to investigational devices including but not limited to: 21 CFR Part 50, Part 54, Part 56, Part 812, Good Clinical Practice (GCP) standards, and Health and Insurance Portability and Accountability Act (HIPAA).

Baylor Research Institute Regulatory Affairs and Data Management departments have quality assurance procedures to ensure that complete, accurate and timely data are collected, that the Investigational Plan requirements are followed and that all complications and adverse events are reported in a timely manner.

Electronic CRFs are used for collecting and recording of data for enrolled subjects at all investigational sites. Investigators or their designees are responsible for the timely completion of these forms. Entered data are reviewed to identify inconsistent or missing data and adverse events. Data problems will be addressed by phone or written communication with the investigational sites and/or during site visits. All forms and data files will be secured to ensure confidentiality. Investigators are to maintain all source documents required by regulation, including diagnostic test reports, laboratory results, completed CRFs, supporting medical records and informed consents. The source documents will be referenced during regular monitoring visits to verify the information documented on the CRFs.

Pre-operative diagnostic tests will be evaluated by the Investigator and other appropriate professionals at the investigational site to determine the subject's eligibility for the clinical study.

25.0 Table of Events (Table 2.0)

	Screening/ Baseline	During Procedure	Discharge	1 Month (-7/+14 days)	6 Month (+/- 30 days)	12 Month (+ 60 days)
Informed Consent	Х					
Medical History	Х					
Physical Exam	Х		Х	Х	х	х
Cardiac Medications	Х		Х	Х	Х	Х
Cardiac Catheterization	х					
CT Scan with contrast	X ¹			X ⁴	X ⁵	
TTE	Х		Х	Х	х	Х
PFT ²	Х					
Chest X-ray	Х		Х	Х		Х
12-Lead ECG	Х		Х	Х		Х
6 Minute Walk Test	Х			Х		х
5 Meter Walk Test	Х					
NYHA Classification	х		х	Х	Х	х
STS Risk Score	Х					
Quality of Life (KCCQ)	х			х	х	х
Intra-Procedure assessments		Х				
Adverse Event Assessment		Х	Х	Х	Х	Х

Table of Events (Table 2.0) continued

Lab Measurements					
CBC and Platelet Count	Х	Х	Х		Х
СМР	Х	Х	Х		Х
BNP	Х	Х	Х		Х
PTT or PT/INR	Х	Х	Х	Х	Х
Blood or urine pregnancy ³	Х				
Plasma Free Hemoglobin			Х	Х	Х
Haptoglobin			X	Х	Х

1. 3D Computed Tomography scan with contrast of chest, heart and peripheral vasculature with assessment of degree and pattern of MAC

2. Pulmonary Function Test within 1 year of consent

- 3. A blood or urine pregnancy test will be performed at screening for females with childbearing potential. A positive pregnancy test will render the subject ineligible for study participation.
- 4. 4D Computed Tomography scan with contrast of the heart to include valve assessment
- 5. 4D Computed Tomography scan with contrast of heart to include valve assessment *if* any of the following have occurred:

A. presence of thrombus on 30 day 4DCT scan

B. Increase in mitral gradient as measured on TTE

C. Clinical deterioration or clinical event including:

i. neurological or peripheral embolic event

ii. Rehospitalization for heart failure

Appendix 2: VALVE ACADEMIC RESEARCH CONSORTIUM DEFINITIONS

TERM	DESCRIPTION
Cardiovascular Mortality	Any of the following criteria:
(M-VARC)	 Death due to proximate cardiac cause (e.g., myocardial
	infarction, cardiac tamponade, worsening heart failure)
	 Death caused by non-coronary vascular conditions such
	as neurological events, pulmonary embolism, ruptured
	aortic aneurysm, dissecting aneurysm, or other vascular
	disease
	 All procedure-related deaths, including those related to
	a complication of the procedure or treatment for a
	complication of the procedure
	 Sudden or unwitnessed death
	 Death of unknown cause
Procedure-related death (M-VARC)	Procedure-related death is defined by any intra-procedural
	events that result in immediate or consequent death (within
	48 hours).

Non-cardiovascular mortality (M-VARC)

Any death in which the primary cause of death is clearly

related to another condition (e.g., trauma, cancer, suicide).

Myocardial Infarction (M-VARC)

Peri-procedural MI (≤ 72 hours after the index procedure): New ischemic symptoms (e.g. chest pain or shortness of breath), or new ischemic signs (e.g. ventricular arrhythmias, new or worsening heart failure, new STsegment changes, hemodynamic instability, new pathological Q waves in at least two contiguous leads, imaging evidence of new loss of viable myocardium or new wall motion abnormality),

AND

Elevated cardiac biomarkers within 72 h after the index procedure consisting of at least one sample postprocedure *with a peak value exceeding 15x upper reference limit (troponin) or 5x for CK-MB. If cardiac biomarkers are increased at baseline* (>99th percentile), a further increase *of at least 50% postprocedure is required* AND the peak value must exceed the previously stated limit.

Spontaneous MI (> 72 hours after the index procedure):

Any one of the following criteria:

Detection of *rise and/or fall of cardiac biomarkers* (preferably troponin) with at least one value above the
 99th percentile URL, *together with evidence of myocardial ischemia with at least one of the following*:

 – Symptoms of ischemia

ECG changes indicative of new ischemia [new ST-T changes or new left bundle branch block (LBBB)]
New pathological Q waves in at least two contiguous leads

 Imaging evidence of new loss of viable myocardium or new wall motion abnormality

2) *Sudden, unexpected cardiac death*, involving cardiac arrest, often with symptoms suggestive of myocardial ischemia, and *accompanied by presumably new ST elevation, or new LBBB, and/or evidence of fresh thrombus by coronary angiography and/or at autopsy*, but death occurring before blood samples could be obtained, or at a time before the appearance of cardiac biomarkers in the blood.

3) *Pathological findings* of an acute myocardial infarction.

Life-threatening Bleeding:

• Fatal bleeding (BARC type 5) OR

• Bleeding in a critical organ, such as intracranial, intraspinal, intraocular, or pericardial necessitating pericardiocentesis, or intramuscular with compartment syndrome (BARC type 3b and 3c) OR

- Bleeding causing hypovolemic shock or severe hypotension requiring vasopressors or surgery (BARC type 3b) OR
- Overt source of bleeding with drop in hemoglobin of \ge 5 g/dL

Bleeding

(M-VARC)

Confidential

Baylor Scott & White Research Institute

or whole blood or packed red blood cells (RBCs) transfusion ≥ 4 units* (BARC type 3b)

Major Bleeding:

- Over bleeding either associated with a drop in the hemoglobin level of at least 3.0 g/dL or requiring transfusion of 2 or 3 units of whole blood/RBC AND
- Does not meet criteria of life-threatening or disabling bleeding

Minor Bleeding:

 Any bleeding worthy of clinical mention (e.g. access site hematoma) that does not qualify as life-threatening, disabling, or major.

Change in serum creatinine (up to 7 days) compared with baseline

- Stage 1 Increase in serum creatinine to 150–200% (1.5–2.0 × increase compared with baseline) or increase of ≥0.3 mg/dL
 (≥26.4 mmol/L) within 48 hours.
- Stage 2 Increase in serum creatinine to 200–300% (2.0–3.0 \times increase compared with baseline)
- Stage 3* Increase in serum creatinine to 300% (>3x increase compared with baseline) or serum creatinine of
 4.0 mg/dL (354 mmol/L) with an acute increase of at least
 0.5 mg/dL (44 mmol/L)
- *Subjects receiving renal replacement therapy are considered to meet Stage 3 criteria irrespective of other criteria

Acute Kidney Injury (M-VARC)

Confidential

Vascular access site and site related	Major Vascular Complications:
complications	 Any thoracic aortic dissection, aortic rupture, annulus
(M-VARC)	rupture, left ventricle perforation, or new apical
	aneurysm/pseudo-aneurysm
	 Access site or access-related vascular injury (dissection,
	stenosis, perforation, rupture, arterio-venous fistula,
	pseudoaneurysm, hematoma, irreversible nerve injury,
	compartment syndrome, percutaneous closure device failure)
	leading to death, major bleeding*, visceral ischemia or
	neurological impairment
	 Distal embolization (non-cerebral) from a vascular source
	requiring surgery or resulting in amputation or irreversible
	end-organ damage
	 The use of unplanned endovascular or surgical intervention
	associated with death, major bleeding, visceral ischemia or
	neurological impairment
	Minor Vascular Complications:
	 Access site or access-related vascular injury (dissection,
	stenosis, perforation, rupture, arterio-venous fistula,
	pseudoaneurysm, hematomas, percutaneous closure device
	failure) not leading to death, major bleeding*, visceral
	ischemia or neurological impairment
	 Distal embolization treated with embolectomy and/or
	thrombectomy and not resulting in amputation or irreversible
	end-organ damage
	• Any unplanned endovascular stenting or unplanned surgical
	, and and a chaot a scaling of an planned surgicul

 Any unplanned endovascular stenting or unplanned surgical intervention not meeting the criteria for a major vascular complication

Confidential

Baylor Scott & White Research Institute

Percutaneous Closure Device Failure:

- Access site or access-related vascular injury (dissection, stenosis, perforation, rupture, arterio-venous fistula, pseudoaneurysm, hematomas, percutaneous closure device failure) not leading to death, major bleeding*, visceral ischemia or neurological impairment
- Distal embolization treated with embolectomy and/or thrombectomy and not resulting in amputation or irreversible end-organ damage
- Any unplanned endovascular stenting or unplanned surgical intervention not meeting the criteria for a major vascular complication

Vascular Complications:

- Major vascular complications:
 - Hematoma at the access site > 6 cm;
 - Retroperitoneal hematoma;
 - Arterio-venous fistula;
 - Symptomatic peripheral ischemia/nerve injury with
 - clinical signs or symptoms and lasting > 24 hours;
 - Vascular surgical repair at catheter access sites;
 - Ipsilateral deep vein thrombus; or
 - Access site-related infection requiring intravenous
 - antibiotics and/or extended hospitalization.

Device failure, defined as the absence of device success, is subclassified as:

- Delivery failure (i.e., technical failure)
- Structural failure: the device does not perform as intended due to a complication related to the device (e.g., fracture,

Device Failure

migration or embolization, frozen leaflet, device detachment, and so on)

 Functional failure: the device performs as intended without complication but does not adequately reduce the degree of MR (MR . moderate [2+], or fails to relieve or creates new mitral stenosis [EROA ,1.5 cm2 or transmitral gradient .5 mm Hg]).

Paravalvular leak

- Major: moderate or severe (2+, 3+, or 4+), or associated with haemolysis, or requiring intervention or surgery
- Minor: trace or mild (1+), without haemolysis

latrogenic atrial septal defect

- Major: significant left-to-right shunt (Qp:Qs ≥2:1) or symptomatic requiring the need for closure
- Minor: nonsignificant shunt that is still present at 26 months

Coronary vessel compression or obstruction

- Angiographic evidence of any reduction in coronary artery luminal diameter or coronary sinus diameter due to either external compression, thrombosis, embolism, dissection, or other cause, subclassified as:
 - Major (250% diameter stenosis) or minor (<50%)
 - Symptomatic or not
 - Requiring treatment or not
 - Transient (intraprocedural only, resolved at procedure end) or persistent

Specific device-related technical failure issues and complications Paravalvular leak

Pericardial effusion

- Major: leading to cardiac tamponade or requiring intervention
- Minor: not leading to cardiac tamponade and not requiring intervention

Conversion to open mitral valve surgery during a transcatheter procedure, subclassified as

- Secondary to mitral valve apparatus damage or dysfunction, requiring surgical valve repair or replacement, or
- Secondary to procedural complications (such as cardiac perforation, removal of an embolized device, and so on)

Device malpositioning

- Ectopic device placement: permanent deployment of a device in a location other than intended
- Device migration: after initial correct positioning, the device moves within its initial position but not leading to device embolization
- Device embolization: the device moves during or after deployment such that it loses contact with its initial position

Device detachment

- Partial: detachment of part of the device from the initial position without embolization
- Complete: detachment leading to device embolization or ectopic device placement

Baylor Scott & White Research Institute Device fracture

- Major: a break, tear, perforation, or other structural defect in the device (stent, housing, leaflet, arm, and so on) resulting in device failure, resulting in recurrent symptoms, or requiring reintervention, or
- Minor: a break, tear, perforation, or other structural defect in the device (stent, housing, leaflet, arm, and so on) not resulting in device failure, not resulting in recurrent symptoms, and not requiring reintervention

Damage to the native mitral valve apparatus

- Chords
- Papillary muscles
- Leaflets
- Mitral annulus

Interaction with non-mitral valve intracardiac structures

- Left ventricular outflow tract obstruction (gradient increase ≥10 mm Hg from baseline)
- Aortic valve regurgitation (2 moderate or 2+)
- Other

Device thrombosis, defined as any thrombus attached to or near an implanted valve, subclassified as:

- Major: occludes part of the blood flow path, interferes with valve function (e.g., immobility of 1 or more leaflets), is symptomatic, or is sufficiently large to warrant treatment, or
- Minor: incidental finding on echocardiography or other

imaging test that is not major

Endocarditis

Any 1 of the following:

- Fulfilment of the modified Duke endocarditis criteria¹¹, or
 - Evidence of abscess, paravalvular leak, pus, or vegetation confirmed as secondary to infection by histological or bacteriological studies during an operation or autopsy.
 - Should be further subclassified by organism, and early (<1 yr) vs. late (>1 yr)

Haemolysis

 The presence of a paravalvular leak on transoesophageal or transthoracic echocardiography plus anaemia requiring transfusion plus increased
 haptoglobin and/or LDH levels; should be confirmed by a haematologist

Other device-specific endpoints

- The number of devices (e.g., clips, neochords) used by intent to achieve the desired reduction in MR
- The need for unplanned use of additional devices (e.g., valves, clips, neochords) as a result of failed device delivery, device detachment, device fracture,

or other device system failure

 If surgery is required, inability to perform mitral valve repair because of the presence of or anatomic changes from the device

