6.0 STUDY OBJECTIVES

6.1 **Primary Outcome Measures:**

- a. Primary objective(s)
 - Primary safety endpoints:

- o Technical success at exit from cath lab/OR
- Device success at 30 days
- Procedural success at 30 days

Technical Success:

- Alive, with
- Successful access, delivery and retrieval of the device delivery system, and
- Deployment and correct positioning (including repositioning/recapture if needed) of the single intended device, and
- No need for additional unplanned or emergency surgery or re-intervention related to the device or access procedure

Device Success:

- Alive and stroke free, with
- Original intended device in place, and
- No additional surgical or interventional procedures related to access or the device since completion of the original procedure (i.e., exit from the cath lab/OR), and
- Intended performance of the device:
 - Structural performance: No migration, embolization, detachment, fracture, hemolysis, thrombosis (including reduced leaflet motion) or endocarditis, etc, and
 - Hemodynamic performance: Maintenance of relief of stenosis or insufficiency without producing the opposite (Stenosis = MVA < 1.5cm2 and MV gradient > 5mmHg, Insufficiency = MR >1+), and
 - Absence of para-device complications (e.g., PVL > mild, need for a PPM, erosion, Annular rupture or AV Groove disruption, LVOT gradient increase > 10mmHg)

Procedural Success:

Device success, and

- No device or procedure related SAE's (Life threatening bleed; major vascular or cardiac structural complications requiring unplanned reintervention or surgery; stage 2 or 3 AKI (includes new dialysis); MI or need for PCI/CABG; severe HF or hypotension requiring IV inotrope, ultrafiltration or mechanical circulatory support; prolonged intubation (> 48 hours)
- •
- 6.2 Secondary objective(s)
 - Device Success (at 6 months and 1 year)

- Subject success 1 year Device Success:
- Alive and stroke free, with
- Original intended device in place, and
- No additional surgical or interventional procedures related to access or the device since completion of the original procedure (i.e., exit from the cath lab/OR), and
- Intended performance of the device:
 - Structural performance: No migration, embolization, detachment, fracture, hemolysis, thrombosis (including reduced leaflet motion) or endocarditis, etc, and

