14.1 ENROLLMENT AND STUDY PROCEDURES

14.2 Baseline/Screening

The following information will be collected for all study subjects prior to procedure. Baseline assessments must be completed within 30 days of subject enrollment unless otherwise specified. Subjects are considered enrolled at the time of initial skin incision.

- A. Society of Thoracic Surgeons (STS) Risk Score Assessment
- B. Medical History and Physical Exam including Cardiac Medications
- C. Cardiopulmonary:
 - 1. Cardiac Catheterization (within 6 months prior to consent)
 - 2. 3D Computed Tomography scan with contrast of chest, heart and peripheral vasculature with assessment of degree and pattern of MAC
 - 3. Transthoracic echocardiogram (TTE)
 - 4. 12 Lead Electrocardiogram (ECG)
 - 5. Chest X-Ray
 - 6. Pulmonary Function Test (PFT) within 1 year prior to consent
- A. Functional Assessments:
 - 1. 6 minute walk test (6MWT)
 - 2. NYHA classification
 - 3. QOL assessments: KCCQ
 - 4. 5 meter walk test (5MWT)
- B. Subject Clinical Laboratory Tests
 - 1. Complete Blood Count (CBC) and platelet count
 - 2. Complete metabolic panel (CMP) including Albumin
 - 3. B-type natriuretic peptide (BNP)
 - 4. PTT or PT/INR (if applicable)

5. A blood or urine pregnancy test will be performed at screening for females with childbearing potential. A positive pregnancy test will render the subject ineligible for study participation.

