14.5 Follow-Up Procedures

Follow-up procedures will be conducted at the intervals specified in Table 1.0. Blood draws will be performed at the specified intervals and according to hospital standard or medication regimen. Subjects will be informed that some of the data that are collected at scheduled followups as well as at unscheduled visits, including the echocardiogram and CT scan may be sent to the respective independent core lab for analysis.

If a subject cannot be reached for a follow-up visit, the investigator will document on the followup data form, the efforts undertaken to contact the subject. These efforts should include 3 attempts of telephone contacts at separate dates and times, and a registered letter. If the subject cannot be reached in any way for their follow-up visits and misses the scheduled visit, new efforts will be undertaken to locate them at subsequent follow-up visits. In the event that the subject's implanted value is explanted, the subject needs to be continued to be followed for the duration of the study.

Follow-up visit intervals are as follows: 30 days (-7/+14 days), 6 months (±30 days), 12 months (+60 days). Additional phone follow-ups may be performed as needed to obtain up to date survival information for use in regulatory submissions.

For all subjects at all visits, the time clock starts on the date of the first implant attempt, whether or not the implant is successful and site visits will be scheduled accordingly.

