19.0 DEVIATIONS FROM THE STUDY PROTOCOL

The Investigator will not deviate from the protocol without the prior written approval of the Sponsor except in medical emergencies or in unforeseen, isolated instances where minor changes are made that will not increase the subject's risk or affect the validity of the study. Any subsequent revisions to the

Confidential

protocol, including the Informed Consent Form and the Case Report Forms, other than very minor revisions, must be approved by the Sponsor, the FDA, and the IRB. In medical emergencies, prior approval for protocol deviations will not be required, but the Sponsor or its designee and IRB must be notified within 5 working days of the incident. Periodic monitoring of protocol compliance will be performed for each site. Deviations will be documented on the appropriate case report form. The sponsor has the right to suspend enrollment at sites deemed to have excessive protocol compliance issues.

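### The only haemolysis definition available for device success asks for raised haptoglobin, which is the wrong direction, and its other marker, LDH, is scheduled at no visit

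*Combined protocol and SAP*

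**What the plan says.** Section 6.1 makes device success at 30 days a primary endpoint, and procedural success contains it. Section 6.2 repeats device success at 6 months and 1 year. Its structural limb reads "No migration, embolization, detachment, fracture, hemolysis, thrombosis (including reduced leaflet motion) or endocarditis", with no definition of hemolysis and no reference to Appendix 2.

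Appendix 2 holds the only definition. It requires a paravalvular leak on echocardiography plus "anaemia requiring transfusion plus increased haptoglobin and/or LDH levels; should be confirmed by a haematologist". The single adjective governs both markers. The same appendix uses haemolysis to grade leaks: a leak associated with it is major, and the lower grade is "Minor: trace or mild (1+), without haemolysis".

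The visit lists in Section 14 and Table 2.0 schedule haptoglobin and plasma free hemoglobin at 1, 6 and 12 months. LDH appears in none of them. The screening panel is given only as "Complete metabolic panel (CMP) including Albumin".

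Three other routes bear on the point:

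- Section 14.5 says "Blood draws will be performed at the specified intervals and according to hospital standard or medication regimen".
- Section 22.9 lists "Hemolysis / Hemolytic Anemia" among anticipated events, and Table 2.0 has adverse events assessed from the procedure onward.
- Section 23.0 limits the analysis to this: "descriptive statistics (e.g. percentage) and plots will be estimated".

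**The concern.** Haptoglobin binds free hemoglobin and is consumed, so it falls in haemolysis. This is basic physiology; the documents do not state the expected direction. The definition asks for a rise. The marker that the trial collects is therefore defined backwards, and the marker that is defined in the right direction is not scheduled.

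The definition matters most where the leak is mild or less, because Section 6 already fails any subject whose leak is greater than mild. Appendix 2 expects haemolysis in that milder group, since it separates trace or mild leaks with haemolysis from those without. Descriptive percentages are the study's only planned output, so correct classification of each subject is what the study has to deliver. In a multi-center study, sites could also classify the same subject differently, depending on whether they follow the written criteria, local LDH results or clinical judgement.

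**Working it through.** The plan states no expected rate, target or power for device success, so there is no figure of its own to reproduce. The check sets the definition against the schedule and then sizes one misclassification.

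**1. Are the two markers scheduled?** (Section 14 visit lists, compared with Table 2.0)

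| Time point | Haptoglobin | Plasma free hemoglobin | LDH |
|---|---|---|---|
| Screening (14.2) | no | no | no |
| Discharge (14.4) | no | no | no |
| 1 month (14.4.1) | yes | yes | no |
| 6 months (14.4.2) | yes | yes | no |
| 12 months (14.4.3) | yes | yes | no |

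Haptoglobin is scheduled at 3 of 5 laboratory time points and LDH at 0 of 5. There is no baseline haptoglobin. Plasma free hemoglobin is collected but is not part of the definition.

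**2. What does the literal laboratory limb do?** Take a transfused subject with a trace or mild leak.

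| True state | Laboratory data | Literal limb | Result |
|---|---|---|---|
| Haemolysis | Haptoglobin low, no LDH drawn | not met | true case missed |
| Haemolysis | Haptoglobin low, local LDH raised | met | correct |
| No haemolysis | Haptoglobin raised | met, pending haematologist | possible false case |
| No haemolysis | Neither raised | not met | correct |

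The error can run both ways.

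**3. Who is exposed?** Subjects with a leak greater than mild already fail device success. Subjects without a leak or without transfusion cannot meet the definition whatever the laboratory shows. The endpoint changes only for transfused subjects with a leak of mild or less and no other failed component.

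**4. Size.** Section 4.0 gives up to 30 subjects. With M missed cases and F false cases, all otherwise successes, the net shift in device success is 100 × (M − F)/30 points.

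- M = 1, F = 0: +3.3 points
- M = 2, F = 0: +6.7 points
- M = 0, F = 1: −3.3 points
- M = 1, F = 1: 0 points

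For scale, 24/30 is 80.0% (exact 95% CI 61.4 to 92.3) and 25/30 is 83.3% (65.3 to 94.4).

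**5. How likely is an exposed true case?** The documents give no rate, so this rests on assumption. If a share p of subjects are true cases in the exposed group, the chance of at least one among 30 is 1 − (1 − p)^30. This is 0% at p = 0, 26.0% at 1%, 59.9% at 3% and 78.5% at 5%. It is the chance that such a case exists, not that it is missed, and it says nothing about false cases.

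**The case against.** The strongest reply is that the effect is small and partly guarded. A haematologist should confirm each case, hemolysis is a listed event, and blood may also be drawn by hospital standard, so an LDH value may exist. Plasma free hemoglobin gives further surveillance. All of this stands, and it rules out the reading that the trial cannot detect haemolysis. It does not mend the definition: the text asks the haematologist to confirm and gives no stated authority to override the criteria, and local LDH would depend on site practice.

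A reader might infer that device success is biased upward. The documents do not support that. A raised haptoglobin would literally meet the limb, so a false case can lower the percentage, and the net sign is not established.

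A reader might also take Section 6 as adopting Appendix 2. It does not say so. Applying the definition to the endpoint is a reasonable inference, because no other definition exists.

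Nor can a text artefact be fully excluded. Neighbouring entries in the extracted appendix show damaged symbols, displaced labels and some corrupted words, and a line break falls directly after the adjective. The sentence reads continuously and nothing points to a lost word, but the original should be checked.

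Finally, correcting the direction schedules no LDH, sets no window between transfusion and blood draw, and leaves 6 months without a blood count. That is fair: the correction makes the scheduled haptoglobin usable but will not capture every case.

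**Conclusion.** The concern holds as an error in an endpoint definition. As worded, the haptoglobin limb is reversed and LDH has no scheduled data, so scheduled measurements cannot correctly satisfy the laboratory limb. The consequence is 3.3 points of device success per misclassified subject at 30 subjects, in either direction. Procedural success moves with it where the subject has no disqualifying event of its own.

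This rests on three things: the extracted wording is faithful, Appendix 2 is meant to govern Section 6, and the subject fails no other component. Zero affected subjects is plausible, and one is small against the confidence interval. No performance goal or decision rule is at stake, so a reader should not infer that a trial conclusion would be reversed. The correction should still be made, because the fault lies in a component of a primary endpoint and is cheap to repair.

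**What to change.** First check the wording against the original PDF. If it stands:

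1. In Appendix 2, change the laboratory limb to *decreased haptoglobin and/or increased LDH levels*, judged by the site laboratory's reference limits. Leave the leak, transfusion and haematologist elements as they are.
2. In Section 6, state that this definition governs hemolysis at 30 days, 6 months and 12 months.
3. Optionally, give the haematologist the scheduled plasma free hemoglobin as supporting evidence.

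No new test or visit is needed, and haptoglobin values already recorded can be re-read. The cost is administrative: under Section 19.0, revisions other than very minor ones "must be approved by the Sponsor, the FDA, and the IRB". Some limits remain. Scheduled haptoglobin may be weeks or months from the transfusion, so the haematologist must weigh timing. There is no baseline value, and reference limits differ between laboratories.
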